## 9.6 Minimal Response

Minimal response (MR) requires all of the following:

- $\geq 25\%$  to  $< 49\%$  reduction in the level of serum monoclonal protein for at least two determinations six weeks apart.
- If present, a 50 to 89% reduction in 24-hour urine monoclonal protein which still exceeds 200 mg/24hr, for at least two determinations six weeks apart.
- 25-49% reduction in the size of plasmacytomas (by clinical or radiographic examinations) for at least six weeks.
- No increase in size or number of lytic bone lesions (development of compression fracture does not exclude response).

*Note:* MR includes participants in whom some but not all criteria for PR are fulfilled providing the remaining criteria satisfy the requirements for MR.

## 9.7 Stable Disease

Stable disease (SD) is defined as not meeting criteria for any other response as defined in this section.

## 9.8 Progressive Disease

Progressive disease (PD) requires one or more of the following:

- $\geq 25\%$  increase in the level of serum monoclonal protein, which must also be an absolute increase of at least 0.5 g/dL, and confirmed on a repeat investigation.
- $\geq 25\%$  increase in 24-hour urine monoclonal protein, which must also be an absolute increase of at least 200 mg/24hr and confirmed on a repeat investigation.
- $\geq 25\%$  increase in plasma cells in a bone marrow aspirate or on trephine biopsy, which must also be an absolute increase of at least 10%.
- $\geq 25\%$  increase in the difference between involved and uninvolved free light chain levels (The absolute increase must be  $\geq 10$  mg/dl)
- Definite increase in the size of existing lytic bone lesions or soft tissue plasmacytomas. A definite increase is defined as at least 50% (and at least 1 cm) increase as measured serially as the sum of the products of the cross-diameters of the lesions.
- Development of new bone lesions or soft tissue plasmacytomas (not including

- compression fracture).
- Development of hypercalcemia (corrected serum calcium > 11.5 mg/dL or 2.8 mmol/L not attributable to any cause other than progressive multiple myeloma).

*Note:* A response of progressive disease nullifies any other concurrent response. For example, at a given time point a participant meets criteria for VGPR but has development of new bone lesions the response is PD not VGPR.

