### **8.0 DURATION OF THERAPY**

#### **8.1 Criteria for Removal from Study**

Treatment may continue until disease progression or clinical relapse, as defined in Sections 9.8 and 9.9 respectively, or until one or more of the following criterion applies:

- Participant withdraws consent
- Holding study drug(s) > 2 continuous weeks for adverse event(s)
- Adverse event(s) that, in the judgment of the Investigator, may cause severe or permanent harm or which rule out continuation of study drug.
- General or specific changes in the participant's condition render the participant unacceptable for further treatment in the judgment of the investigator
- Suspected or confirmed pregnancy
- Major violation of the study protocol
- Participant lost to follow-up
- The PI decides to remove the participant from study for any reason
- Death
- The treating center decides to close the study

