## 9.5 Partial Response

Partial response (PR) requires all of the following:

- $\geq 50\%$  reduction in the level of the serum monoclonal protein for at least two determinations performed a minimum of six weeks apart.
- Reduction in urine monoclonal protein by either  $\geq 90\%$  or to  $\leq 200$  mg for at least two determinations performed a minimum of six weeks apart.
- If present,  $\geq 50\%$  reduction in the size of soft tissue plasmacytomas (by clinical or radiographic examinations) for at least six weeks.
- If serum and urine monoclonal protein are unmeasurable, a  $\geq 50\%$  decrease in difference between the involved and uninvolved free light chain levels is required in place of monoclonal protein criteria (The absolute decrease must

- be  $\geq 10$  mg/dl)
- If serum and urine monoclonal protein are unmeasurable and serum free light chain is unmeasurable, a  $\geq 50\%$  reduction in plasma cells is required in place of monoclonal protein provided that baseline bone marrow plasma cell percentage was  $\geq 30\%$

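### Section 9.8 lets a single unconfirmed free light chain rise score progression, although serum and urine M-protein rises must be confirmed

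*Combined protocol and SAP*

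**What the plan says.** Section 9.8 opens with "Progressive disease (PD) requires one or more of the following", so each limb is sufficient alone. The serum M-protein limb needs a 25% rise, "which must also be an absolute increase of at least 0.5 g/dL, and confirmed on a repeat investigation". The urine limb needs a 25% rise, "which must also be an absolute increase of at least 200 mg/24hr and confirmed on a repeat investigation". The light chain limb needs a 25% "increase in the difference between involved and uninvolved free light chain levels (The absolute increase must be" at least 10 mg/dl. It says nothing about a repeat and is not limited to participants followed by light chains.

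The note closing Section 9.8 adds: "A response of progressive disease nullifies any other concurrent response". Section 8.1 ties treatment to the same definition: "Treatment may continue until disease progression or clinical relapse, as defined in Sections 9.8 and 9.9".

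Section 10.0 schedules serum free light chains on Day 1 of each cycle and on Day 15 of Cycle 1, with no footnote restricting the row by M-protein measurability. In Section 9.5, light chains enter partial response under the condition "If serum and urine monoclonal protein are unmeasurable". They then replace the M-protein criteria, and that limb states no second determination. Section 15.2 counts progression as a PFS event and ends duration of response at the earliest documented progression.

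**The concern.** Of the three M-protein and light chain limbs in Section 9.8, two are protected against a single aberrant value and one is not. The unprotected one is measured in everyone at every cycle.

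Take a participant whose serum M-protein has fallen by more than half. One light chain result over both thresholds scores that participant as progressed. The concurrent response is nullified, and PFS and duration of response take an event at that date. M-protein responses need two determinations at least six weeks apart, so an event inside that window can also remove a success from the primary endpoint. Phase II is small (17 participants in Section 5.3, 24 in Section 16.0; that conflict is a separate matter), so each misclassified participant counts.

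**Working it through.** No figure in the plan depends on this rule, so there is none to reproduce. The check compares the text and adds a bounded illustration.

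**Text, limb by limb (Section 9.8)**

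| Limb | Thresholds | Guard against a single value |
|---|---|---|
| Serum M-protein | 25% and 0.5 g/dL | repeat required |
| Urine M-protein | 25% and 200 mg/24 hr | repeat required |
| Free light chain difference | 25% and 10 mg/dl | none |
| Marrow plasma cells | 25% and 10% absolute | none |
| Lesions or plasmacytomas | growth of 50% and 1 cm, or new lesions | none |
| Hypercalcemia | above 11.5 mg/dL | must not have another cause |

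Light chains are thus the only blood or urine limb with neither a repeat nor an attribution guard. Marrow and lesion assessments also lack a repeat, but Section 10.0 does not schedule them every cycle. Sections 9, 10, 15 and 16 contain no rule that fills the gap.

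**Draws exposed before confirmation**

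- Day 1 draws are 28 days apart. Counting from a first qualifying value at day 0, draws fall at days 28 and 56. Six weeks is 42 days, so the first scheduled confirmation is day 56. One draw, day 28, lies strictly between; counting the confirmation visit makes two.
- From a first value on Cycle 1 Day 15, Cycle 2 Day 1 is 14 days later and Cycle 3 Day 1 is 42 days later. Again one draw lies between.

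**Illustration**

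Let q be the chance per draw of a rise over both thresholds without tumour progression. The documents give no value; q = 1% to 3% is an assumption.

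- One draw: q = 1% to 3%.
- Two independent draws: 1 − (1 − q)² = 2.0% at q = 1% and 5.9% at q = 3%.
- If an independent repeat must agree, the per-draw chance becomes q² = 0.01% to 0.09%.

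**Effect on the primary decision**

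Under the Section 16.0 rule (24 participants, 8 or more successes) and a true response rate of 40%, power is P(X ≥ 8) = 80.8%. Losing 1% of responses gives a rate of 0.40 × 0.99 = 0.396 and power 79.7%. Losing 3% gives 0.40 × 0.97 = 0.388 and power 77.4%. In expectation, 0.1 to 0.3 of 9.6 responders are lost.

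**The case against.** The strongest points on the other side, and what stands of each:

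- **The thresholds already filter noise.** The 10 mg/dl floor equals the light chain difference that Section 3.1.1 requires for measurable disease at entry. This stands and argues for a small q. However, the serum and urine limbs have absolute floors too and still require a repeat.
- **Light chain response is unconfirmed as well.** Section 9.5 states no second determination for a light chain partial response. This stands. Confirming only progression would tilt a single-arm trial towards response, so the remedy must cover both directions.
- **Other limbs lack confirmation.** This is true of marrow and lesions, but they are not scheduled every cycle.
- **The primary endpoint is barely touched.** This stands: the note in Section 9.8 reaches only a concurrent response, so one already confirmed is kept.

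A reader might go further and infer that Sections 9.5 and 9.8 contradict each other, so that light chain progression should apply only where M-protein is unmeasurable. The documents do not support that. Partial response requires all its criteria, whereas progression requires any one. The example in the Section 9.8 note scores progression from new bone lesions in a participant whose other criteria meet very good partial response, so progression on a marker other than the responding one is intended. Restricting the limb is a trade-off, because light-chain escape may be real progression.

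A reader might also argue that renal impairment makes false rises likely, since Section 3.1.5 admits creatinine clearance just above 15 ml/min. Nothing in the documents links renal function to fluctuation in the light chain difference.

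**Conclusion.** The gap is real and specific: one unconfirmed light chain value suffices for progression, while serum and urine rises must be "and confirmed on a repeat investigation". The main effect is on PFS and duration of response. The primary response count is exposed only before confirmation, with an illustrative loss of 1-3% of responses (2-6% if the confirmation visit is counted). That range rests wholly on the assumed q, on 28-day draws and, for two draws, on independence.

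Compounding the same q over 12 monthly draws would give 1 − (1 − q)¹² = 11.4% to 30.6%. A reader might take this as the expected share of false progressions. It should not be read that way: the rate has no source in the documents, independence across draws is unverified, and most of those draws fall after a response could have been confirmed. The case for change rests on the uneven rule and the low cost of evening it, not on a demonstrated number of false events.

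**What to change.** For scoring response, PFS and duration of response:

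1. In Section 9.8, require the light chain rise to be confirmed by a repeat, as for serum and urine, with progression dated at the first of the two values. State how a rise with no repeat sample is scored.
2. In Section 9.5, require two determinations for the light chain limb of partial response, so that both directions are held to the same standard.
3. Leave the limb open to all participants, whether or not M-protein is measurable.

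Because Section 8.1 links treatment to Section 9.8, the sponsor should reconcile those passages with the revised scoring rule. No treatment-stopping rule is proposed here.

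Cost: a clause in each of two sections. A light chain progression call waits for one repeat of a blood test already drawn each cycle, and a light chain partial response resting on one value would no longer count. Dating at the first value leaves the event time of a confirmed progression unchanged. Neither the sample size nor the decision cutoff changes.

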## **9.9 Clinical Relapse**

Clinical relapse (i.e. progressive disease requiring alternate myeloma treatment) requires one or more of the following:

- Decrease in hemoglobin  $\geq 2$  g/dl not attributable to any cause other than progressive multiple myeloma
- Increase in creatinine by  $\geq 2$  mg/dl not attributable to any cause other than progressive multiple myeloma
- Other worsening laboratory result, or clinical condition that the treating physician determines is not attributable to any cause other than progressive multiple myeloma

## **9.10 Relapse from Complete Response**

Relapse from a complete response requires a prior CR or sCR as described above and subsequently developing one or more of the following:

- Reappearance of serum or urinary paraprotein on immunofixation or routine electrophoresis excluding oligoclonal immune reconstitution for at least two determinations.
- $\geq 5\%$  plasma cells in the bone marrow aspirate or biopsy.

## 10.0 STUDY CALENDAR

Assessment *	Screening a	Cycles 1 through 6						Cycles 7 and beyond				End of Study b	Follow-up c	
		D1	D2	D8	D9	D15	D16	D1	D8	D15	D22			
Sign informed consent	X													
Medical & treatment history	X													
Vital signs d	X	X	X	X	X	X	X	X	X	X	X	X		
Physical exam e	X	X 						X						
Toxicity assessment	X	X	X	X	X	X	X	X	X	X	X	X	X	
CBC w/ differential	X	X		X		X		X	X	X	X	X	X	
Chemistries f	X	X	X	X	X	X	X	X	X	X	X	X	X	
PT/INR & PTT	X	X 												
SPEP & IFIX g	X	X 				X 		X					X	
24-hour urine total protein, UPEP, & IFIX gh	X	X 				X 		X					X	
Serum free light chains	X	X 				X 		X					X	
Quantitative immunoglobulins (IgA, IgG, IgM)	X	X 				X 		X					X	
Beta-2 microglobulin	X	X 						X					X	
Serum $\beta$ HCG j	X	X						X					X	
EKG & Chest x-ray	X													
MUGA or Echo m	X													
Imaging for plasmacytoma assessment km	X												X 	
Skeletal survey m	X												X 	
Bone marrow biopsy & aspirate n	X												X 	
Correlative samples o	X												X 	
Carfilzomib administration		X	X	X	X	X	X	X	X	X	X	X		
PLD administration				X										
Dexamethasone administration p		X	X	X	X	X	X	X	X	X	X	X		
Follow-up for survival														X

\* All assessments allowed a window of +/- 2 days for scheduling issues (such as holidays)

a: Screening period is D-21 though D1 prior to Carfilzomib dose

b: End of study must be within 30 days of last dose of study drug

c: Follow-up takes place every 3 months for up to 18 months or until resolution or stabilization of adverse events, whichever is longer

d: To be done within 1 hour prior to carfilzomib administration.

e: Physical exam includes height, weight, BSA, performance status, neurological assessment and plasmacytoma assessment if indicated .

f: Chemistries include Complete Metabolic Panel with Renal and Hepatic Panels, LDH, Magnesium, Phosphorous, Uric Acid.

g: SPEP = serum protein electrophoresis, IFIX=immunofixation, UPEP= urine protein electrophoresis.

h: All participants must complete 24 hour urine at screening and for confirmation of CR or VGPR if necessary. Additional serial 24-hour urines only required for participants with  $\geq 0.2g/24$  hours of monoclonal protein at screening.

j: Required only in women of childbearing potential; 2 negative test results required before study drug dosing on Cycle 1 Day 1.

k: Only required if clinically indicated. Imaging can include X-ray, CT, MRI, PET, etc.

m: To be repeated on study when clinically indicated.

n: Bone marrow aspirate and core biopsy for differential, cytogenetics, and fluorescent *in situ* hybridization (FISH) studies. To be repeated on study for confirmation of CR or sCR.

o: To be repeated on study whenever a bone marrow biopsy and aspirate is performed.

p: Only for patients treated in part 2 of phase 1 or phase 2.

1: Not required to be repeated in Cycle 1 if screening assessment was within 7 days of Day 1.

2: Only during Cycle 1.

3: Optional. If patient is willing and able.

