## 3.0 PARTICIPANT SELECTION

### 3.1 Inclusion Criteria

A participant must meet all of the following criteria to be eligible for enrollment.

- 3.1.1** Histologically confirmed diagnosis of multiple myeloma with a measurable disease parameter at time of screening. A measurable disease parameter is defined as one or more of the following:
- Serum monoclonal protein  $\geq 0.5$  g/dl.
  - 24 hour urine monoclonal protein  $\geq 0.2$  g/24 hour
  - Serum free light chain ratio  $> 5x$  normal ratio with an absolute difference of 10mg/dl between the involved and uninvolved free light chain.
  - Soft tissue plasmacytoma  $\geq 2$  cm measurable by either physical examination and/or applicable radiographs (e.g. MRI, CT, etc).
  - Bone Marrow Plasma Cells  $\geq 30\%$ .
- 3.1.2** Documentation of at least one line of prior myeloma therapy now with relapsed or refractory disease requiring re-treatment.
- 3.1.3**  $\geq 18$  years of age at time of signing the informed consent.

*Note:* No dosing or adverse event data are currently available on the use of carfilzomib in combination with PLD in participants  $< 18$  years of age. Thus, children and adolescents are excluded from this study but will be eligible for future pediatric phase 2 combination trials.

- 3.1.4** Performance status of ECOG  $\leq 2$  or Karnofsky  $\geq 60$  % (see Appendix A and B).

*Note:* Participants with lower performance status based solely on bone pain secondary to multiple myeloma will be eligible.

- 3.1.5** Required Laboratory Values
- ALT (SGPT) and AST (SGOT)  $< 2.5$  x the upper limit of the institutional normal value (ULN).
  - Total bilirubin  $\leq 1.5$  x ULN.
  - ANC  $\geq 1,000$ .
  - Hemoglobin  $\geq 8$  g/dl.
  - Platelets  $\geq 50,000$ .
  - Creatinine clearance  $> 15$  ml/minute using Cockcroft-Gault formula (See Appendix C).
  - For those participants receiving warfarin (Coumadin), unfractionated heparin, or low-molecular weight heparin therapy, the applicable

coagulation parameter that is being monitored must be within the accepted therapeutic ranges for those indications.

*Note:* Transfusions and/or growth factor dependent participants are not excluded if the above parameters can be achieved with such support.

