## 12.0 CORRELATIVE STUDIES

Bone marrow and peripheral blood samples will be taken prior to treatment, at time of complete response, and/or at end of study.

The following samples will be collected at all time points:

- Bone marrow aspirate: 6-10 mL divided between two EDTA (lavender top) tubes.
- Peripheral blood for viable PBMC: 60 mL collected in 6 large EDTA (lavender top) tubes.
- Peripheral blood for plasma: 10 mL collected in 1 EDTA (lavender top) tube.

Bone marrow aspirate samples will be pooled, and mononuclear cells will be purified over Ficoll. Resulting BM mononuclear cells will be divided into 1) viable cells cryopreserved at  $10^7$ /vial, and 2) cell pellet for nucleic acid. Plasma and from bone marrow will be divided into 2mL aliquots and frozen at  $-80^{\circ}\text{C}$ .

Peripheral blood mononuclear cells (PBMC) will similarly be isolated by Ficoll preparation from the pooled peripheral blood lavender top tubes and will be viably cryopreserved.

Plasma will be divided into 2mL aliquots and frozen at  $-80^{\circ}\text{C}$ .

Fresh PBMC or BM mononuclear cells may also be used for correlative studies at the discretion of the principal investigator.

All samples are to be delivered to the Siteman Cancer Center Tissue Procurement Core ([name], Director) during their normal operating hours. Specimens will be identified by initials and study number at the Tissue Procurement Core, and samples will be processed appropriately.

Contact information for questions regarding sample procurement only:

[name]., Ph.D.  
Siteman Cancer Center Tissue Procurement Facility  
BJC Institute of Health  
[name]  
[contact]  
[contact]  
Email: [[contact]](mailto:[contact])

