### **15.0 ENDPOINTS**

#### **15.1 Primary Outcome Analyses**

The primary endpoint for each arm of the phase II portion of this trial is the proportion of confirmed tumor responses. A confirmed response is defined to be a CR, VGPR, or PR noted as the objective status. Response will be evaluated using up to 12 cycles of treatment. All participants meeting the eligibility criteria who have signed a consent form and have begun treatment will be evaluable for response.

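### A participant can qualify on marrow plasma cells alone and is then judged for PR on marrow change, yet no required on-treatment marrow can show a PR that falls short of CR

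*Combined protocol and SAP*

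**What the plan says.** Four parts of the combined protocol and SAP bear on this.

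- **Eligibility (3.1.1).** "A measurable disease parameter is defined as one or more of the following". Five parameters follow: serum protein, urine protein, serum free light chains, soft tissue plasmacytoma, and "Bone Marrow Plasma Cells" at 30% or more. Any one is enough.
- **Response (9.5).** If the serum and urine proteins and the free light chains are all unmeasurable, a 50% or greater "reduction in plasma cells is required in place of monoclonal protein provided that baseline bone marrow plasma cell percentage was" at least 30%. The threshold is the same as in 3.1.1, so the plan foresees marrow-only participants.
- **Schedule (10.0).** The row "Bone marrow biopsy & aspirate" is marked at screening and at end of study, with nothing in the treatment-cycle columns. Footnote n gives the only on-study repeat: "To be repeated on study for confirmation of CR or sCR". The end-of-study mark carries footnote 3: "3: Optional. If patient is willing and able".
- **Scoring (9.7, 15.1).** Stable disease is the residual category for anyone who meets no other definition. For the primary endpoint, "All participants meeting the eligibility criteria who have signed a consent form and have begun treatment will be evaluable for response". CR, VGPR and PR count as successes. No rule covers a participant whose deciding assessment was never made.

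**The concern.** For a marrow-only participant the PR criterion exists on paper, but no required visit measures it. Blood and urine are tested on Day 1 of every cycle, but in this participant those tests cannot show a fall of 50%. The one required on-study marrow is tied to confirming CR or sCR, a deeper response than PR. The end-of-study marrow is voluntary and comes after treatment ends, often at progression, and under 9.8 progression overrides any concurrent response.

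The primary endpoint is the response proportion in a small single-arm phase II, and the go/no-go decision turns on a count of successes. A true PR that goes unmeasured becomes stable disease and stays in the denominator. That pulls the observed proportion down and makes an active regimen harder to recognise.

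**Working it through.** **Does any provision require a marrow that could show PR?**

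| Provision | Does it require an on-treatment marrow for PR? |
|---|---|
| 10.0, cycle columns | No marrow marked |
| 10.0, footnote n | Only to confirm CR or sCR |
| 10.0, footnote m (repeat if clinically indicated) | Attached to MUGA/Echo, plasmacytoma imaging and skeletal survey, not to marrow |
| 10.0, footnote 3 | End of study only, voluntary |
| 10.0, footnote o | Adds correlative samples when a marrow is done; orders none |
| 11.0, marrow form due after each cycle | A submission deadline; orders no procedure |
| 1.7, samples at time of response | Correlative only, and narrowed by 12.0 |

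Section 12.0 reads: "Bone marrow and peripheral blood samples will be taken prior to treatment, at time of complete response, and/or at end of study". No row supplies a marrow for PR.

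**Plan's own figure.** Section 16.0 gives a null proportion of 20%, a target of 40%, 24 participants, success at 8 or more, and significance level 0.10. It states no numerical power. By exact binomial:

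- 24 participants, 8 or more: P(Bin(24, 0.20) ≥ 8) = 0.0892, within a nominal 0.10; power P(Bin(24, 0.40) ≥ 8) = 0.808.
- Section 5.3 instead treats 17 participants and calls 5 or fewer successes ineffective, so success is 6 or more: P(Bin(17, 0.20) ≥ 6) = 0.1057; power P(Bin(17, 0.40) ≥ 6) = 0.736.

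The disagreement between 17 and 24 is a separate matter. Both rules are carried through here.

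**Effect of unscorable participants.** Let k be the number of marrow-only participants in the phase II set. The documents do not give k, so 0 to 3 is an assumed range. Assume also that none of the k can be scored as a success and that the others respond independently with probability p. Then

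P(go) = P(Bin(n − k, p) ≥ r), with (n, r) = (24, 8) or (17, 6).

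| k | 24/≥8, p = 0.40 | 17/≥6, p = 0.40 | 24/≥8, p = 0.20 | 17/≥6, p = 0.20 |
|---|---|---|---|---|
| 0 | 0.808 | 0.736 | 0.089 | 0.106 |
| 1 | 0.763 | 0.671 | 0.072 | 0.082 |
| 2 | 0.710 | 0.597 | 0.056 | 0.061 |
| 3 | 0.650 | 0.514 | 0.043 | 0.044 |

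One such participant costs 0.808 − 0.763 = 0.045 of power under the 24 rule and 0.736 − 0.671 = 0.065 under the 17 rule. Two cost 0.098 and 0.139. The chance of a false go also falls, so the error is towards rejecting an active regimen. The k = 3 row is an outer bound: 3/17 is 18% of the smaller sample. All rows overstate the loss to the extent that some of the k can still be scored.

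**The case against.** A reader might infer that every marrow-only participant is a non-responder by default. The documents do not support that.

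- **CR route.** In truly non-secretory disease the protein tests are negative throughout, so marrow is the outstanding CR criterion. An investigator could take a marrow under footnote n, and the same sample could show a 50% fall. The timing is left to judgement, but the route exists.
- **VGPR route.** Unmeasurable does not mean absent. A protein visible on immunofixation but not on electrophoresis can satisfy the first VGPR option in 9.4 without a marrow, and VGPR is a success.
- **Discretionary marrow.** Nothing forbids an extra marrow; footnote n can be read as a minimum, and section 11.0 lists a marrow form each cycle.

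The first two points stand and limit the claim to likely loss of PRs. The third shows only that a marrow is permitted. In an open single-arm trial the primary endpoint should not depend on who happens to be biopsied.

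A reader might also infer that PFS is biased upward in these participants. That is too strong. Bone lesions, plasmacytomas and hypercalcemia count as progression under 9.8, and 9.9 adds clinical relapse, which is a PFS event under 15.2. Blood counts and chemistries recur throughout treatment. At most, progression in some of these participants is detected later.

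Finally, k is undocumented and may be 0, in which case nothing is lost. That is fair, and it governs the size of the problem rather than its existence.

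**Conclusion.** The gap is real: the plan defines a primary-endpoint criterion that no required on-treatment visit measures. A marrow-only participant who reaches PR but not CR is likely, though not certain, to be scored as stable disease and kept in the denominator.

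The size is uncertain. Each such participant who cannot be scored lowers the chance of recognising a regimen with a true 40% response rate by roughly 4 to 8 percentage points over the range shown, more under the 17-participant rule than under the 24. This rests on an assumed k, on none of the k being scorable, and on independent responses at 40% in the rest. It does not support saying that the decision rule can no longer detect an active regimen. The point deserves correction because the change is cheap, not because a large effect has been shown.

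**What to change.** In section 3.1.1, with a matching sentence in 5.3, state that for phase II, and for phase I participants at the MTD who are counted toward it, marrow plasma cells of 30% or more may not be the sole measurable parameter. Require at least one other 3.1.1 parameter: serum protein, urine protein, serum free light chains, or a soft tissue plasmacytoma. The first three are in the per-cycle schedule, and footnote m allows plasmacytomas to be re-imaged on study. Marrow-only participants stay eligible for phase I, where the endpoint is DLT.

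This needs no additional marrow procedure. The cost is wording in two sections and the exclusion from phase II of the few participants with marrow-only (non-secretory) disease, including any treated at the MTD in phase I who would otherwise have counted. The phase II population narrows slightly, and accrual may be a little slower.
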